9. BENEFITS

The dual energy CT scan will be interpreted by a radiologist, a physician with expertise in CT imaging. A formal report will be placed permanently in the electronic medical records. It is possible that the radiologist may detect liver cancer or another important but unexpected finding. Clinically significant unexpected imaging findings will be communicated by phone with the gastroenterologist per standard of care at UAB. The gastroenterologist will discuss these findings with the participants.

10. ALTERNATIVES

This is not a treatment study. The alternative is to not participate in this study.

11. DATA AND IMAGE ANALYSIS

11.1 Clinical Evaluation:

Baseline clinical and laboratory data (**Table 1**) will be gathered by the study coordinator and entered into a password-restricted and secure web-based REDCap database. Data from the post-endoscopy and post-DECT questionnaires will be entered into the REDCap database.

11.2 Endoscopy Evaluation:

All patients will undergo standard of care upper gastrointestinal endoscopy in The Kirklin Clinic or Highlands Hospital endoscopy suites for surveillance of gastroesophageal varices. The endoscopists will report the grade of esophageal varices: grade 0 = none, grade 1 = small (≤ 5 mm), and grade 2 = large (> 5 mm). The endoscopists will also record the presence or absence of a red wale or red spot sign, presence or absence of gastric varices, presence or absence of signs of portal gastropathy, presence or absence of gastritis, duodenitis, or a gastric or duodenal ulcer, and presence or absence of active bleeding (and location if present). The hepatologist will also be contacted to confirm the substage of cirrhosis, which includes the information from the surveillance endoscopy.

11.3 Image Evaluation:

11.3.1 DECT Image Acquisition:

Table 2. Relevant Clinical and Laboratory Data

- **Demographics:** age, gender, race, ethnicity, body mass index
- **Comorbidities:** Charlson comorbidity index
- **Cirrhosis etiology:** AH, HBV, HCV, NAFLD, cryptogenic, autoimmune, and other
- **Baseline cirrhosis substage:** compensated without varices, compensated with varices, and decompensated
- **Baseline serum labs:** total bili, AST, ALT, albumin, INR, platelets, creatinine, calculated MELD and FIB-4 scores
- **Study procedure date:** date of endoscopy and DECT
- **Procedure complications:** From DECT or endoscopy
- **2-year follow up to track liver-related events:** ascites, hepatic encephalopathy, bleeding varices, intervention for varices, TIPS, liver transplant, HCC, or death

Study participants will undergo DECT imaging of the liver in the late arterial and in the portal venous phases. The late arterial phase will be performed with bolus tracking and occur 20 seconds after triggering. The portal venous phase will also be performed with bolus tracking and occur 40 seconds after triggering. Both phases will utilize our standard-of-care DECT image acquisition protocol. Imaging will be performed per standard of care, with the patient in the supine position with arms above the head. No oral contrast will be administered. Noncontrast and delayed phase imaging will not be performed to reduce the radiation dose.

11.3.2 DECT Image Evaluation:

The DECT images will be interpreted according to our standard of care with a dictated report by a board-certified abdominal radiologist. The radiologist interpreting the study will be asked to interpret the study using a structured reporting template that includes the grade of esophageal varices, presence or absence of other varices, presence or absence and stage of HCC, severity of ascites, and patency of liver vasculature. The structured report template is currently in use by multiple abdominal faculty and can be easily acquired by any abdominal radiologist at UAB through Powerscribe, our routine dictation reporting system.

Each DECT study will be de-identified per standard technique using OsiriX. A coded identifier will be applied to each image, and the images will be stored on OsiriX and on a secure password-restricted Server Message Block (SMB), a virtual hard drive established for Radiology Clinical Research that has restricted access to defined users. Study personnel will use the Liver Surface Nodularity (LSN) Software to measure the LSN score on all patients, while remaining blinded to the clinical data. [name] or [name] will review all of the exported images and confirm a satisfactory measurement for each patient, with revising of measurements that are not satisfactory.

11.3.3 Inter-observer Analysis:

After all patients are recruited (N=50), a designated co-investigator will set up reading session for the other radiology co-investigators (N=4 radiology residents and N=4 radiology faculty). A training video will be prepared and used to instruct the readers on how to view the images, conduct the reading sessions, and record the data in a REDCap.

Each reader will interpret the images independently in timed reading sessions, while blinded to clinical data. The most important data point will be the grade of esophageal varices, though readers will also evaluate for presence or absence of other varices, presence or absence and stage of HCC, severity of ascites, and patency of liver vasculature.

12. 2-YEAR FOLLOW UP:

The primary purpose of screening for gastroesophageal varices is to prevent future variceal bleeding and the associated high mortality. Detection of bleeding events is therefore a critical component of the study. The patients will be contacted by phone by the study coordinator at 1- and 2-years post endoscopy to capture information on complications of cirrhosis, particularly bleeding episodes and treatment of high-risk gastroesophageal varices. If the patient has a visit to the hepatologist, the interview may alternatively be conducted at that time per patient preference. The electronic medical records will also be searched for complication of cirrhosis and bleeding episodes. The study coordinator will conduct the interviews and record all data in a REDCap database. The patients will be discharged from the study after the 2 year follow up interview.

13. STATISTICAL CONSIDERATION:

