13.2 Statistical analysis plan

Patient and imaging characteristics will be summarized and compared using appropriate summary statistics, e.g. mean and standard deviation for continuous variables, frequency and percentage for categorical variables, and extensive exploratory data analysis and data visualizations will be utilized to assess diagnostics, identify outliers, and validate assumptions.

Receiver operating characteristic (ROC) analysis will be used in Aim 1 to estimate the accuracy of DECT for differentiating no varices from any varices and for differentiating no and small varices from large varices in Aim 1. Sensitivity, specificity, accuracy, and AUC along with their two-sided 95% CI will be presented separately. The grade of varices (0, 1, 2) on DECT will be correlated with the grade of varices on endoscopy (0, 1, 2) using weighted Kappa coefficient for categorical data (Aim 2.2).

The MIXED effect model will be used in Aim 2.1 to estimate the ICC for the inter-observer agreement for the detection of any varices and high-risk varices on dual energy CT. Reader experience and subject will be the two random effects in the model used for interobserver variability. The intraclass correlation coefficient (ICC) will be defined as the ratio between subject variance and the sum of variances for subject, reader experience and error term. ICC values will be characterized as very poor (0 to <0.20), poor (0.20 to <0.40), moderate (0.40 to <0.60), good (0.60 to <0.80), and very good (0.80 to 1.00).

Time to development of bleeding varices (or hepatic event) will be modeled in Aim 2.3 using Cox proportional hazards models with clustered sandwich estimators to account for within and between cluster correlations. Cause specific proportional subhazards analysis while accounting for competing risks (e.g. gastroesophageal banding) and adjusting for covariates will be utilized to assess the association between endoscopic findings and DECT findings and time to developing individual vs. any hepatic complications.

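### Section 13.2 does not name the DECT read behind the primary accuracy and the weighted kappa; one of the two candidates follows endoscopy with no stated blinding to it

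*Combined protocol and SAP*

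**What the plan says.** Section 11.3 describes two sources of a DECT variceal grade.

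- **Clinical report (11.3.2).** "The DECT images will be interpreted according to our standard of care with a dictated report by a board-certified abdominal radiologist". The structured template includes the esophageal variceal grade. There is one report per patient, and no blinding is mentioned.
- **Research reads (11.3.3).** Four residents and four faculty read all scans after recruitment is complete. "Each reader will interpret the images independently in timed reading sessions, while blinded to clinical data".

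Section 11.3.2 also states blinding for the liver surface nodularity measurement: study personnel "measure the LSN score on all patients, while remaining blinded to the clinical data".

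Section 6 places DECT after endoscopy, on the same day or within two weeks.

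Section 13.2 then uses DECT results in three places:

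- Aim 1: "Receiver operating characteristic (ROC) analysis will be used in Aim 1 to estimate the accuracy of DECT for differentiating no varices from any varices", and likewise for large against no or small varices. No read or reader is named.
- Weighted kappa (labelled Aim 2.2): "The grade of varices (0, 1, 2) on DECT will be correlated with the grade of varices on endoscopy". Again no read is named.
- Inter-observer agreement: "The MIXED effect model will be used in Aim 2.1 to estimate the ICC for the inter-observer agreement". This is the only analysis in 13.2 that is tied to multiple readers.

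**The concern.** The primary endpoint is the AUROC of DECT with endoscopy as the reference standard. A three-level variceal grade involves judgement, and a reader who knows the endoscopic grade may be drawn towards it. That would raise the AUROC, sensitivity, specificity and kappa together, and the confidence intervals would not show it.

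The hypotheses are thresholds on the estimate: above 0.90 (any) and above 0.95 (high-risk) in the opening summary, and above 0.90 for both in section 13.1. The only null value given for a test is 0.5, which any useful read will exceed. The conclusion will therefore rest on the point estimate and its interval, which is where this bias would act.

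There is a second, separate problem. With two sets of grades and no rule, the read can be picked after both are known.

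**Working it through.** **1. The texts side by side**

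| DECT measurement | Section | Timing | Blinding stated | Use stated in 13.2 |
|---|---|---|---|---|
| Clinical report, 1 per patient | 11.3.2 | after endoscopy | none | none named |
| Session reads, 8 × 50 = 400 | 11.3.3 | after all are recruited | to clinical data | Aim 2.1 ICC only |
| Nodularity score | 11.3.2 | not given | to clinical data | Aim 2.4 |

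Neither source of a grade is assigned to Aim 1 or to the kappa. If the session reads are meant, there is no rule for combining eight grades per patient.

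**2. The plan's own figure**

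Section 13.1 claims more than 95% power for AUC 0.90 against 0.5, with 34 patients with and 16 without varices, one-sided 0.05. The Hanley-McNeil standard error is

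SE² = [A(1−A) + (n1−1)(Q1−A²) + (n0−1)(Q2−A²)] / (n1·n0), with Q1 = A/(2−A) and Q2 = 2A²/(1+A).

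This gives SE 0.0884 at A = 0.5 and 0.0429 at A = 0.90. Power = Φ((0.40 − 1.645 × 0.0884)/0.0429) = Φ(5.9), above 99.9%. The claim reproduces and is not in dispute. It treats the data as one DECT result per patient.

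**3. Illustration of scale (assumed inputs)**

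The documents give no DECT accuracy and no rate of access to the endoscopy result, so both are assumed here. The patient mix is the planned 16/16/18. Let P be the table of DECT grade (0, 1, 2) given endoscopy grade:

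- 60% exact: [.65 .25 .10; .25 .50 .25; .10 .25 .65]
- 70% exact: [.75 .20 .05; .20 .60 .20; .05 .20 .75]
- 80% exact: [.80 .15 .05; .10 .80 .10; .05 .15 .80]

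A share f of wrong grades is changed to the endoscopy grade: P′ = (1−f)P + f·I. AUROC = Pr(positive graded higher) + ½ Pr(tie).

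Worked case, 80% and f = 0.25, any varices (34 vs 16):

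- Grades without varices: [.85 .1125 .0375].
- Grades with varices, rows 1 and 2 of P′ weighted 16:18: [.0551 .4596 .4853].
- Higher: .4596 × .85 + .4853 × .9625 = .8577.
- Tie: .0551 × .85 + .4596 × .1125 + .4853 × .0375 = .1168.
- AUROC = .8577 + .0584 = .916, against .887 at f = 0.

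All cases, any / large (large is 18 vs 32):

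| Exact agreement | f = 0 | f = 0.10 | f = 0.25 | f = 0.50 |
|---|---|---|---|---|
| 60% | .779 / .775 | .801 / .798 | .835 / .831 | .890 / .888 |
| 70% | .854 / .850 | .869 / .865 | .891 / .888 | .928 / .925 |
| 80% | .887 / .884 | .899 / .896 | .916 / .914 | .945 / .943 |

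The shift runs from +0.01 (80%, f = 0.10) to +0.11 (60%, f = 0.50). Three of the nine leakage cases cross 0.90, for both contrasts. None reaches 0.95.

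Two comparisons give context. At 80% and f = 0 the 95% half-widths are 1.96 × 0.046 = 0.090 (any) and 1.96 × 0.055 = 0.109 (large), so most of these shifts are within sampling error. Against 0.5, with the standard error at 0.5, z at f = 0 is already 3.16 to 4.47 over the three tables, so that test is passed with or without leakage.

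**The case against.** **The bias is conditional.** It needs the clinical report to supply Aim 1, the radiologist to see the endoscopy grade, and that knowledge to change the DECT grade. No passage establishes any of the three. The protocol records the grade in the study database and scans at separate imaging centres. This stands: what is shown is an unnamed read, not a biased one. A reader might infer from the layout that the clinical report is the Aim 1 read, because it sits under the image-evaluation heading while the session reads sit under inter-observer analysis. The text permits that but does not say it. Using the session reads for Aim 1 would fit the plan equally well.

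**The illustration builds in its own direction.** This also stands. Six of nine cases do not cross 0.90, so a reader should not infer that the hypotheses would falsely appear met. Under this model the 0.95 target never does. That a shift lies within sampling error is a weaker defence, because a systematic shift is not reflected in the interval.

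**The session reads are already protected.** Largely so. Section 11.2 has the hepatologist "confirm the substage of cirrhosis, which includes the information from the surveillance endoscopy", which places variceal status within the clinical data, and "Each DECT study will be de-identified per standard technique using OsiriX". The three-level endoscopic grade and the clinical DECT report are not explicitly covered. De-identification is described for the stored research images, so it cannot be assumed to cover the clinical dictation.

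**Routine reporting may be the intended target.** Accuracy of routine reports and accuracy of research readers are different quantities, and either is a legitimate choice. The plan still has to say which, and whether that read is blinded to endoscopy.

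**Naming the session reads is not a complete cure.** Correct. Nothing prevents a faculty session reader from having dictated the clinical report on the same scan, and de-identification does not remove recall of the images.

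**Conclusion.** The omission is certain: section 13.2 names no DECT read for the Aim 1 accuracy measures or the weighted kappa, and one of the two candidates follows endoscopy without stated blinding. The consequence is possible rather than shown. The plan as written allows the primary estimate to come from a read open to the reference result, or from a read selected after the fact.

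The size of any inflation cannot be derived from the documents. The range above rests wholly on assumed agreement tables and assumed leakage, and it should not be used to argue severity. A statement that the radiologist is unblinded, or that the primary result will be inflated, would go beyond the text.

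The change should be made because it affects the primary endpoint and blinded reads of the same scans are already planned. Confidence is high for the omission only.

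**What to change.** **In 13.2:**
- State that Aim 1 and the weighted kappa use the blinded reads already planned in 11.3.3.
- Before the sessions start, fix which readers count (for example the four faculty, or all eight) and how their reads are combined.
- Specify a confidence interval that allows for several reads per patient. A reader-averaged AUROC with a bootstrap over patients and readers is one option, though four to eight readers give limited information on reader variation.
- Report the accuracy of the clinical report as secondary, labelled as not blinded.

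**In 11.3.3:**
- State that the blinding covers the endoscopic grade and the clinical DECT report.
- Leave out of the primary analysis any session read by a reader who dictated the clinical report on that scan.

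**Alternative.** If the sponsor keeps the clinical report as the primary read, state that its variceal grade is recorded blinded to the endoscopy result. This may be harder to arrange, because the report is filed in the medical record for patient care (section 8.5).

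**Cost.** A few sentences and an analysis of reads already planned, with no new scans, readers or patients. The primary result waits for the reading sessions and describes research readers rather than routine reporting. If residents are included, it reflects mixed experience.

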13.1 Sample size justification

[name] (co-investigator and biostatistician) will conduct and supervise all statistical analyses. This is a prospective study to determine the accuracy of dual energy CT for detecting any varices and high-risk varices in patients with cirrhosis presenting for upper gastrointestinal endoscopy. The endpoint of the primary objective is accuracy which is determined by the Area Under the Curve (AUC) using Recursive Operating Characteristics (ROC) analysis (AUROC). Based on published studies ^{1,2,3} in patients with detected gastroesophageal varices, we will observe 32%, 32%, and 36% with no, small, and large varices, respectively. In order to test the hypothesis: the accuracy (AUROC) of DECT will be >0.90 for detecting any and high-risk varices in a prospective pilot study that uses endoscopy as the reference standard, we plan to enroll 50 patients such that we will have 16/50, 16/50, and 18/50 with no, small, and large varices. This size of the study will have $>95\%$ power to detect any varices, e.g. (16+18)/50 small and large varices with $AUC >=0.90$ comparing to null hypotheses of $AUC=0.5$ (not detect any) using a one-sided z-test at a significance level of 0.05 controlled false positive rates at 1%.

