Cirrhosis leads to portal hypertension and development of gastroesophageal varices, which are the most common cause for bleeding in cirrhosis and a major cause of death. The American Association for the Study of Liver Disease (AASLD) recommends screening endoscopy every 2 years to evaluate for gastroesophageal varices, and annual surveillance for those with small varices on endoscopy. Unfortunately, endoscopy is costly, requires sedation, is poorly tolerated, is subject to high inter-observer variability, and is associated with risks that include bleeding, esophageal injury and aspiration. Noninvasive methods for evaluation of gastroesophageal varices are needed. CT is noninvasive, rapid, less expensive than endoscopy, requires no sedation, provides a quantitative measure of the size of the varices, and allows for assessment of para-esophageal varices, varices in other body locations, ascites, other signs of portal hypertension, patency of liver vasculature, and detection, diagnosis and staging of hepatocellular carcinoma. Single-Energy CT (SECT) has relatively high accuracy in prospective studies for detection of any and large varices but is associated with suboptimal contrast opacification of gastroesophageal varices. Dual-Energy CT with the GE scanners with GSI Xtream (DECT) improves the contrast-to-noise ratio by 60% compared to SECT and is currently standard of care at UAB for evaluation of cirrhosis. The primary objective of this study is to determine the accuracy of DECT for detecting any varices and high-risk varices. We hypothesize that the accuracy (AUROC) of DECT will be >0.90 and >0.95 for detecting any and high-risk varices in a prospective pilot study (N=50) that uses endoscopy as the reference standard. This will be a single-center pilot observational prospective IRB-approved study. We will enroll 50 adult patients presenting to UAB Endoscopy for surveillance endoscopy to detect and grade gastroesophageal varices.

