2. BACKGROUND AND RATIONALE

Cirrhosis leads to portal hypertension and development of gastroesophageal varices, which are the most common cause for bleeding in cirrhosis and a major cause of death. Bleeding varices have a 6-week mortality of 15%-25%.^{1,2} About 50% of patients with cirrhosis have varices, and 30% have large varices (>5 mm) that are high risk for bleeding.³

The American Association for the Study of Liver Disease (AASLD) recommends screening endoscopy every 2 years to evaluate for varices, and annual surveillance for those with small varices on endoscopy.⁴ Patients at a high risk of bleeding with large varices, small varices and red wale signs (an endoscopic finding), or small varices and decompensated cirrhosis proceed to treatment such as prophylactic band ligation and beta blockers.^{5,6,7} Conversely, patients with no varices or small varices (≤ 5 mm) continue surveillance efforts by endoscopy to monitor for development of large varices.^{3,7,8} Unfortunately, endoscopy is costly, requires sedation, is poorly tolerated, is subject to high inter-observer

variability, cannot detect other signs or portal hypertension or para-esophageal varices that are at risk for future bleeding events, and is associated with risks that include bleeding, esophageal injury and aspiration.⁹ Many of these factors contribute to poor patient compliance with AASLD recommendations.

Noninvasive methods for detecting, grading, and risk stratification of esophageal varices are needed. Imaging tests such as ultrasound elastography to measure liver stiffness have been proposed as a method to predict the presence of varices but have insufficient accuracy to eliminate the need for endoscopy.¹⁰ An ideal biomarker to screen for esophageal varices would be part of the routine standard of care of patients with cirrhosis, noninvasive, rapid, less expense than endoscopy, highly accurate, highly reproducible, and would require no sedation, provide a quantitative measure of the size of the varices, provide a mechanisms to assess the risk of future bleeding, allow for an assessment for other signs of portal hypertension, and provide other benefits to the patient (e.g. detect ascites and HCC and assess liver vasculature).

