3. OBJECTIVES

3.1 Primary Objective

To determine the accuracy of dual energy CT for detecting any varices and high-risk varices in patients with cirrhosis presenting for upper gastrointestinal endoscopy.

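### Section 13.1 sizes the study to test AUROC >0.90, but its >95% power is against AUC = 0.5 and for any varices only; the high-risk threshold also differs between the synopsis and 13.1

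*Combined protocol and SAP*

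**What the plan says.** - **Objective (3.1):** "To determine the accuracy of dual energy CT for detecting any varices and high-risk varices in patients with cirrhosis". Any and high-risk varices stand side by side as primary targets.
- **Synopsis:** the hypothesis is that "the accuracy (AUROC) of DECT will be >0.90 and >0.95 for detecting any and high-risk varices in a prospective pilot study (N=50" patients). The threshold is 0.90 for any varices and 0.95 for high-risk varices.
- **Sample size (13.1), purpose:** "In order to test the hypothesis: the accuracy (AUROC) of DECT will be >0.90 for detecting any and high-risk varices", 50 patients are planned, with 16, 16 and 18 expected to have no, small and large varices.
- **Sample size (13.1), power:** power above 95% is stated for any varices at an AUC of 0.90 or more, "comparing to null hypotheses of $AUC=0.5$ (not detect any) using a one-sided z-test at a significance level of 0.05". The sentence ends with "controlled false positive rates at 1" per cent, which is not explained. No power or precision is given for high-risk varices.
- **Analysis (13.2):** one contrast is none versus any varices. The other is "for differentiating no and small varices from large varices in Aim 1". On reporting: "Sensitivity, specificity, accuracy, and AUC along with their two-sided 95% CI will be presented separately". No test against 0.90 or 0.95 is named, and no expected interval width is given.

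**The concern.** In the hypothesis, 0.90 is the value to be exceeded. In the power statement, 0.90 is the assumed truth and 0.5 is the value to be exceeded. These are different questions, yet 13.1 offers the second as the reason for an N chosen to answer the first. It is the only statistical justification for 50 patients, so the protocol has no statement of what N=50 can show about its own hypothesis, and none at all for high-risk varices.

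The two high-risk thresholds add a separate problem. An observed high-risk AUC of 0.93 would lie above the value in 13.1 and below the one in the synopsis, so the plan does not settle how the result should be read.

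**Working it through.** **Inputs.** From 13.1: N = 50; 34 with any varices versus 16 with none; 18 large versus 32 none or small; one-sided alpha 0.05; null 0.5; alternative 0.90. The 18/32 split follows the contrast in 13.2. True AUCs above 0.90 are my assumptions, since the documents give none.

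**Formulas.** Hanley-McNeil, with m patients having the target condition and n without:

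SE² = [A(1−A) + (m−1)(Q1−A²) + (n−1)(Q2−A²)] / (mn), where Q1 = A/(2−A) and Q2 = 2A²/(1+A).

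Example, A = 0.90, 34/16: Q1 = 0.8182 and Q2 = 0.8526, so SE² = (0.09 + 33×0.0082 + 15×0.0426)/544 = 0.00184 and SE = 0.0429.

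| True AUC | SE, any (34/16) | SE, large (18/32) |
|---|---|---|
| 0.50 | 0.0884 | 0.0859 |
| 0.90 | 0.0429 | 0.0519 |
| 0.95 | 0.0294 | 0.0373 |
| 0.97 | 0.0224 | 0.0291 |
| 0.98 | 0.0181 | 0.0238 |

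Power with the null SE = Φ[(A1 − A0 − 1.645·SE0)/SE1]. Power with the alternative SE = Φ[(A1 − A0)/SE1 − 1.645].

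**1. The plan's own figure.** Any varices, 0.90 against 0.5: (0.40 − 1.645×0.0884)/0.0429 ≈ 5.9, so power is above 99.9%. The stated >95% is correct. It is also above 99.9% for large varices: (0.40 − 1.645×0.0859)/0.0519 ≈ 5.0. Both stay above 99.9% at a one-sided alpha of 0.01, so the unexplained 1% does not alter this.

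**2. What passes that test.** The critical observed AUC is 0.5 + 1.645×0.0884 = 0.645 for any varices and 0.5 + 1.645×0.0859 = 0.641 for large varices.

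**3. Power against 0.90.** At a true AUC of exactly 0.90 it equals alpha, 5%, by definition. Above that (null SE to alternative SE):

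| Assumed true AUC | Any (34/16) | Large (18/32) |
|---|---|---|
| 0.95 | 24-52% | 17-38% |
| 0.97 | 49-93% | 30-78% |
| 0.98 | 70-99.7% | 41-96% |

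Example, any varices at 0.95: null SE, (0.05 − 1.645×0.0429)/0.0294 = −0.70, giving 24%; alternative SE, 0.05/0.0294 − 1.645 = 0.06, giving 52%.

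The upper ends are optimistic. In simulation (continuous binormal scores, 34/16, 5,000 replicates), a Wald test using the estimated SE rejected about 13% of the time when the true AUC was 0.90, against a nominal 5%. The Obuchowski binormal variance with the null SE gives less than the lower ends: 15%, 26% and 38% for any varices, and 13%, 20% and 26% for large varices.

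**4. Expected two-sided 95% intervals (A ± 1.96·SE).**
- Observed 0.90, any: 0.90 ± 0.084, or 0.82-0.98.
- Observed 0.90, large: 0.90 ± 0.102, or 0.80-1.00 (the upper limit computes to 1.002).
- Observed 0.95: lower limits 0.95 − 0.058 = 0.89 (any) and 0.95 − 0.073 = 0.88 (large).

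The Background gives another case mix: "About 50% of patients with cirrhosis have varices, and 30% have large varices". With 25/25 and 15/35, the SEs at 0.95 are 0.0324 and 0.0406 and the lower limits are 0.89 and 0.87, so the picture does not hinge on the mix in 13.1.

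**The case against.** The null of 0.5 is printed in the power sentence, so nothing is hidden. One can read 0.90 as the expected value and 0.5 as the null, and on that reading the statement is coherent and true. The study is a pilot whose objective is to determine accuracy, and 13.2 plans estimates with intervals and no test against 0.90. The omitted high-risk power is also above 99.9% on the stated test.

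Most of this stands. It shows that no planned analysis depends on the mismatch and that the remedy is wording. It does not remove the mismatch, because 13.1 itself ties N=50 to testing >0.90. A plan built on estimation is properly justified by expected interval width, which is absent.

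Three stronger readings are tempting but not supported:
- **That the >95% is wrong.** It is arithmetically correct for the test described.
- **That 50 patients cannot support >0.90.** This depends on the true AUC, which the documents do not give. At an assumed 0.98, power is 70-99.7% for any varices and 41-96% for large varices.
- **That 16 or 17 patients would have been enough for the test against 0.5.** This is a rough normal approximation. At 16 patients (11 versus 5), simulation of the same test gives about 91%, not 95%. Nor does 13.1 claim that 50 is a minimum.

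**Conclusion.** The concern holds as a mismatch between the stated hypothesis and the stated power, together with a conflict between two thresholds. The >95% shows that DECT would be distinguished from chance; it is not evidence that N=50 can establish AUROC >0.90. At a true AUC of 0.95 the power for that is roughly a quarter to a half for any varices and lower for large varices, and at an observed 0.95 the lower confidence limit falls just short of 0.90 for both contrasts.

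The direction is firm; the percentages are not. They rest on assumed true AUCs, on a normal approximation that is rough near 1, and on a continuous score, whereas the DECT reading is a three-level grade. The high-risk figures apply to the large-varices contrast in 13.2; the Background also counts some small varices as high risk.

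A reader might infer that the study's results are compromised. They are not: the planned estimates and intervals are unaffected. The fault lies in what the protocol says the pilot can show. It should be fixed, and the fix is small.

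**What to change.** 1. In 13.1, say that the >95% is power against chance only. Justify N=50 by the approximate expected two-sided 95% intervals for both contrasts, for example those in step 4 at observed AUCs of 0.90 and 0.95. Note that a three-level grade makes them approximate, and leave the interval method to the trial statistician.
2. Use one high-risk AUROC threshold in the synopsis and in 13.1.
3. Define or delete the 1% false-positive phrase (minor).

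The cost is a few sentences in the synopsis and 13.1, with no added patients and no change to conduct or analysis. The downside is a less favourable stated justification.
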